9.1 Analysis sets

The following analysis sets will be used in the analyses:

Enrolled set: All patients who are enrolled are included in the Enrolled set.

Safety set: The Safety set includes all patients who received at least one dose of study drug.

Full Analysis set: The Full Analysis set includes all patients who received at least one dose of study drug.

9.2 Patient demographics and other baseline characteristics

Demographics and other Baseline characteristics will be collected at Screening (Visit 1) or at Baseline (Visit 2) prior to first study drug administration for the efficacy and PRO measurements. Summary statistics will be provided for demographic and Baseline characteristics. Data will be summarized for the overall population as well as for the 3 pre-defined subpopulations with absolute counts and relative frequencies for categorical variables and with mean, standard deviation, minimum, median, and maximum for continuous variables.

Patient background information (medical history and current medical conditions) will be summarized by MedDRA primary SOC and preferred term. Summaries for psoriasis specific medical history and cardiovascular medical history will also be provided.

9.3 Treatments

The analysis of study treatment data will be based on the Safety set.

Duration (days) of exposure to study drug will be summarized. The number of secukinumab injections will be presented by visit and cumulatively.

Patients who prematurely discontinue the study drug will be listed along with the reason for discontinuation.

Compliance will be calculated in percent as the number of injections administered divided by the number of injections scheduled according to the protocol.

9.3.1 Prior and concomitant medications

Prior and concomitant medications will be summarized by prior psoriasis treatment subpopulation in separate tables.

Prior medications are defined as treatments taken and stopped prior to first dose of study drug. Any medication given at least once between the day of first dose of study drug and the last day of study will be a concomitant medication, including those which were started pre-Baseline and continued into the treatment period or beyond.

Medications will be presented in alphabetical order, by ATC codes and grouped by anatomical main group. Tables will also show the overall number and percentage of patients receiving at least one treatment of a particular ATC code and at least one medication in a particular anatomical main group.

9.4 Analysis of the primary variable

9.4.1 Variable

The primary analysis variable is the proportion of patients achieving a DLQI 0/1 response at Week 16 in 3 pre-defined subpopulations and in the overall study population.

The analysis of the primary variable will be based on the Full Analysis set.

9.4.2 Statistical model, hypothesis, and method of analysis

The primary analysis of this study will be descriptive without any formal group comparisons or hypothesis testing. The absolute and relative frequencies of patients achieving a DLQI 0/1 response at Week 16 will be calculated for the subpopulations defined above as well as for the overall study population. For the proportions, (descriptive) 95% CIs will additionally be reported.

9.4.3 Handling of missing values/censoring/discontinuations

The last observation carried forward (LOCF) method will be applied to the continuous variables of DLQI score, PASI score and IGA mod 2011 score that are missing after Baseline regardless to the reason for missing data (e.g. premature study discontinuation, missed visit, administrative issues). The binary response variables based on DLQI score, PASI score and IGA mod 2011 score will be derived from these imputed values, this means that a patient with missing values will be counted as a non-responder unless he already achieved the respective response criterion at the last available measurement.

Any missing individual items are treated as missing data. Cases for which a weekly score cannot be calculated (less than four completed days) will not be included in the analysis. The percent of missing and missing patterns for each item will be assessed.

9.4.4 Sensitivity analyses

No sensitivity analysis will be performed.

9.5 Analysis of secondary variables

9.5.1 Efficacy variables

All secondary objectives (as defined under [Section 2.2](#)) will be analyzed descriptively, similarly to the primary endpoint. Relative and absolute frequencies will be presented for categorical variables and mean, SD, median, minimum and maximum will be presented for continuous variables.

9.5.2 Safety variables

Analysis of safety data will be based on the Safety set.

Adverse events

The assessment of safety will be based primarily on the frequency of AEs and SAEs. SAEs suspected by the Investigators to be related to the prescribed medication will be summarized as appropriate.

The only AEs that will be counted will be treatment-emergent AEs (TEAEs). A TEAE is defined as any AE that develops after initiation of the study treatment or any event already present that worsens following exposure to the study treatment. This definition is not used by the Investigator, but rather is used in the analysis and reporting of clinical trial data. A patient with multiple AEs within a body system will only be counted once towards the total of this body system.

The incidence of AEs (new or worsened) will be summarized by primary SOC, preferred term, severity and relationship to study drug. In addition, the incidence of death, SAEs, and AEs leading to discontinuation will be summarized separately by primary SOC and preferred term.

All AEs will be displayed by group and patient.

Vital signs

All vital signs (including height and weight) will be summarized by prior psoriasis treatment group and visit and listed by group, patient and time. Analysis of the vital sign measurements using summary statistics for the change from Baseline for each post-Baseline visit will be performed.

Clinical laboratory evaluations

The summary of laboratory evaluations will be presented for the hematology, clinical chemistry, and fasting laboratory tests. Descriptive summary statistics for the change from Baseline to each visit will be presented. These descriptive summaries will be presented by laboratory test and prior psoriasis treatment group. Changes from Baseline will only be summarized for patients with both Baseline and post Baseline data.

Shift tables will be provided for all parameters to compare a patient's Baseline laboratory evaluation relative to the most extreme observed value during the treatment phase. For the shift tables, the normal laboratory ranges will be used to evaluate whether a particular laboratory test value was normal, low, or high for each visit value relative to whether or not the Baseline value was normal, low, or high. These summaries will be presented by laboratory test and treatment group. Shifts will be presented by visit as well as for most extreme values post-Baseline.

Physical examinations

All physical examination data will be listed by prior psoriasis treatment group, patient and visit and summary statistics will be provided by prior psoriasis treatment group and visit.

Pregnancy tests

Serum and urine pregnancy tests where applicable will be summarized and listed.

9.5.3 Health-related quality of life

The analysis of the HR-QoL assessments in [Section 6.6.1](#) is described in the SAP.

9.5.4 Resource utilization

Not applicable.

9.5.5 Pharmacokinetics

Not applicable.

9.5.6 Pharmacogenetics/pharmacogenomics

Not applicable.

9.5.7 Biomarkers

If a biomarker sub study is performed, details will be described in a separate study protocol.

9.5.8 PK/PD

Not applicable.

9.6 Interim analyses

An interim analysis describing the self-reported Baseline characteristics and HR-QoL of patients prior to treatment may be performed for this study after LPFT. Details will be described in the Statistical Analysis Plan (SAP).

9.7 Sample size calculation

The study aims to estimate primarily the effect of 16 weeks treatment with secukinumab 300 mg on the QoL of the overall study population as well as within the 3 pre-defined subpopulations. It is expected that 40% of the overall study population will fulfil the criteria for the definition of subpopulation A; 40% will fulfil the criteria for subpopulation B; and 20% will fulfil the criteria for subpopulation C.

The DLQI 0/1 response rate in the overall population treated with secukinumab 300 mg s.c. is expected to be around 70% at Week 16; however, it may vary within those pre-defined subpopulations. A total of 323 patients are required to estimate the response rate of DLQI 0/1 with a precision (= 95% CI) of 5% if the true response rate is about 70% in the smallest subpopulation. To ensure that this precision is achieved in the 3 subpopulations (defined in [Section 3.1](#)), which consist of 20% to 40% of the overall study population, 1 615 patients in total should be recruited into this trial.

10 Ethical considerations

[figure not shown]

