5.2 Treatment subpopulations

Eligible patients will be stratified at Baseline according to previous exposure to treatment in 3 subpopulations:

- **Subpopulation A:** 646 patients who are **naïve to any systemic treatment**, e.g. patients failing or intolerant to previous topical treatment, including narrow band ultraviolet B (UVB) but never exposed to any systemic treatment, with or without contraindications to the use of conventional systemic treatment and in need of a first systemic treatment.
- **Subpopulation B:** 646 patients who have been **previously exposed to at least one conventional systemic therapy**; either because of failure or intolerance to their previous conventional systemic treatment, they are in need of first biologic systemic treatment.
- **Subpopulation C:** 323 patients who have been **previously exposed to at least one biologic systemic therapy**; either because of failure or intolerance to their previous biologic systemic treatment, they are in need of a different biologic systemic treatment.

All patients will be assigned to receive the same treatment regimen:

- **Secukinumab 300 mg regimen:** Secukinumab 300 mg s.c. (supplied in single boxes each containing 2 × PFS of the 150 mg dose for s.c. injection) self-administered at Baseline, once weekly at Week 1, 2 and 3, and thereafter at 4-weekly intervals starting Week 4 until Week 48 inclusive.

The treatment administration schedule is presented in [Table 5-1](#) and the treatment administration schedule is presented in [Table 6-2](#).

Table 5-1 Overview of treatment during the study

Treatment Period 1 (Baseline to Week 16)	
(Self-administration at Study Center)	(Self-administration at Home)
Baseline & Weeks 1, 2, 3, 4, 8, and 12	None
Treatment Period 2 (Week 16 to Week 52)	
(Self-administration at Study Center)	(Self-administration at Home)
Week 16, 20, 24, 36 and 48	Week 28, 32, 40 and 44

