Patients who discontinue study drug should not be considered withdrawn from the study (except if the patient withdraws their informed consent).

See [Section 6](#) for the required assessments of these patients after study drug discontinuation. Patients who are discontinued from the study will not be replaced.

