8.5 Adjudication committee

Not applicable.

9 Data analysis

Summary statistics for continuous variables will include N, mean, standard deviation, minimum, median, maximum. Summary statistics for discrete variables will be presented in contingency tables and will include absolute and relative frequencies.

If not otherwise specified, p-values will be presented as two-sided p-values and 2-sided CIs will be displayed.

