2.14 Interim analysis

An interim analysis describing the self-reported baseline characteristics and HR-QoL of patients prior to treatment will be performed for this study after LPFT.

The interim analysis will be based on the Safety set.

Patient screening phase disposition, demographics, baseline disease characteristics, baseline IGA mod 2011, PASI and PROs will be presented as described in [Section 2.3](#).

Other medical history and prior medications and non-drug therapies will not be part of the interim analysis.

3 Sample size calculation

The study aims to estimate primarily the effect of 16 weeks treatment with secukinumab 300 mg on the QoL of the overall study population as well as within the 3 pre-defined subpopulations. It is expected that 40% of the overall study population will fulfil the criteria

for the definition of subpopulation A; 40% will fulfil the criteria for subpopulation B; and 20% will fulfil the criteria for subpopulation C.

The DLQI 0/1 response rate in the overall population treated with secukinumab 300 mg s.c. is expected to be around 70% at Week 16; however, it may vary within those pre-defined subpopulations. A total of 323 patients are required to estimate the response rate of DLQI 0/1 with a precision (= 95% CI) of 5% if the true response rate is about 70% in the smallest subpopulation. To ensure that this precision is achieved in the 3 subpopulations (defined in Section 3.1), which consist of 20% to 40% of the overall study population, 1 615 patients in total should be recruited into this trial.

4 Change to protocol specified analyses

According to the protocol all data from physical examinations should be summarized and listed. As these data are only collected in the source data (see Section 6.5.1 of the protocol) this will not be analyzed.

5 Appendix

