5.6 Statistical models

5.6.1 Primary analysis

The primary analysis of this study will be descriptive without any formal group comparisons or hypothesis testing.

Summary statistics for discrete variables will be presented in contingency tables and will include absolute and relative frequencies. Confidence intervals will be derived as well based on the score method including continuity correction [Newcombe (1998)]:

With z as (1-alpha/2)-quantile of the standard normal distribution (SAS: $z=PROBIT(1-alpha/2)$), n as total number of subjects (i.e. number of subjects in the denominator), and p as estimated crude incidence (number of subjects with event / n) it is $q = 1-p$.

Then the lower limit is for $p > 0$, ($L = 0$ for $p = 0$),

$$L = \max \left(0, \frac{2np + z^2 - 1 - z \sqrt{z^2 - 2 - \frac{1}{n} + 4p(nq + 1)}}{2(n + z^2)} \right)$$

and the upper limit is for $p < 1$, ($U = 1$ for $p = 1$)

$$U = \min \left(1, \frac{2np + z^2 + 1 + z \sqrt{z^2 + 2 - \frac{1}{n} + 4p(nq - 1)}}{2(n + z^2)} \right)$$

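### Does the sample size overstate precision because 323 patients give a half-width of 5.0 points with the simple normal formula but 5.1 points with the interval the SAP will report?

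*Protocol*

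**What the plan says.** Protocol 9.7 justifies the trial's size by precision alone: "A total of 323 patients are required to estimate the response rate of DLQI 0/1 with a precision (= 95% CI) of 5" per cent, "if the true response rate is about 70% in the smallest subpopulation". It expects about 70% overall and adds "however, it may vary within those pre-defined subpopulations". Subpopulation C is expected to be 20% of the trial, so the total is set at 1,615: "To ensure that this precision is achieved in the 3 subpopulations". SAP section 3 repeats this text. Neither place names an interval formula or says that the 5% is a half-width.

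Protocol 5.2 plans 646, 646 and 323 patients for A, B and C. Protocol 5.6.2 adds: "Patients who are discontinued from the study will not be replaced".

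For the analysis, the opening of Protocol section 9 says that "2-sided CIs will be displayed" unless otherwise specified. SAP 5.6.1 fixes the method: "Confidence intervals will be derived as well based on the score method including continuity correction", with the formula printed. Protocol 9.4.2 and SAP 2.5.2 make the primary analysis descriptive, with no hypothesis test.

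**The concern.** In a study without a hypothesis test, the width of the confidence interval is the only quantitative ground for the number of patients. One would expect the planning calculation to use the interval that will be reported. Here it appears not to. A continuity-corrected score interval is somewhat longer than the Wald interval at the same n, so a size that only just meets 5 points with Wald will miss it with the reported method.

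Subpopulation C is planned at exactly the calculated minimum, with no allowance for losses. The text concedes that the rate may differ between subpopulations, yet speaks of ensuring the precision in all three. If the shortfall were large, the primary estimate in C would be less precise than the plan promised, and the stated basis for the trial's size would not stand.

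**Working it through.** **Inputs.** Rate p = 0.70, target d = 0.05 and n = 323 (Protocol 9.7); subpopulation sizes 646, 646 and 323 (Protocol 5.2); two-sided 95% interval, z = 1.95996, z² = 3.8415; interval formula from SAP 5.6.1.

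**1. The plan's own figure.** With the Wald half-width,

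n = z² p(1 − p)/d² = 3.8415 × 0.70 × 0.30 / 0.0025 = 322.68, rounded up to 323.

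Then 323/0.20 = 1,615 and 0.40 × 1,615 = 646. All three planned sizes reproduce. This also settles the meaning of the 5%: read as a half-width, it gives 323 exactly.

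**2. The interval to be reported, n = 323 and p = 0.70.** Here 2np = 452.2 and 2(n + z²) = 653.68.

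- Lower limit: [452.2 + 3.8415 − 1 − z√(z² − 2 − 1/n + 4p(nq + 1))] / 653.68 = (455.04 − 1.95996 × 16.612)/653.68 = 0.6463.
- Upper limit: [452.2 + 3.8415 + 1 + z√(z² + 2 − 1/n + 4p(nq − 1))] / 653.68 = (457.04 + 1.95996 × 16.564)/653.68 = 0.7488.

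The interval is 64.63% to 74.88%, and half its length is 5.13 points. It is asymmetric: 5.37 points below the estimate and 4.88 above. The score interval without the correction has a half-length of 4.97 points, so the continuity correction accounts for the excess.

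**3. Size needed for 5.0 points with that method.** n = 339 gives 5.002 and n = 340 gives 4.994, so 340 in C, which is 17 more than planned.

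**4. Dependence on the rate, n = 323.**

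| Rate | SAP interval, half-length (points) | Wald half-width (points) |
|---|---|---|
| 50% | 5.57 | 5.45 |
| 60% | 5.47 | 5.34 |
| 65% | 5.33 | 5.20 |
| 70% | 5.13 | 5.00 |
| 73% | 4.97 | 4.84 |
| 75% | 4.86 | 4.72 |
| 80% | 4.50 | 4.36 |

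The choice of method adds 0.12 to 0.14 points throughout. The rest of the movement comes from the rate and would occur with either method. It goes both ways: from 73% upwards in this table, the reported interval meets 5 points.

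**5. The other groups.** At n = 646 the SAP interval has a half-length of 3.60 points at 70% and at most 3.92 (at 50%). At n = 1,615 it is 2.26 points at 70%.

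**6. Does non-replacement shrink C?** Only slightly. The Full Analysis set is everyone dosed (Protocol 9.1) or everyone dosed with at least one post-baseline efficacy assessment (SAP 2.2). LOCF is applied after baseline whatever the reason for the gap (SAP 2.5.3). A patient who discontinues after a post-baseline DLQI score stays in the denominator. As an illustration with an assumed n, even 310 analysed patients would give 5.24 points at 70%.

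**The case for a change.** The strongest argument for acting is that 323 rather than 322 was chosen by treating 5.00 points as a limit, and with the reported method that limit is not met even at exactly 70%. The SAP interval first falls to 5.0 points or less at 235 responders of 323 (234 gives 5.004, 235 gives 4.987). If the true rate is 70%, the chance of that is 15%, against 53% for Wald. At 60% and 50% the half-length rounds to 5.5 and 5.6, which is no longer 5. SAP section 3 also looks carried over without a check against SAP 5.6.1: it points to a Section 3.1 for the subpopulations, which is the protocol's numbering.

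The arithmetic stands, as does the observation that the planning text does not name its formula. The inference does not. The contrast of 15% with 53% comes from cutting at exactly 5.000, where 0.017 points separate failure from success. The plan fixes an expected width and gives no assurance of attaining it, so even Wald succeeds only about half the time. The widening at 60% and 50% is almost wholly an effect of the rate, and the stated precision is conditional on a rate near 70%. The sentence about ensuring precision refers back to that conditional statement; its purpose is to scale up from the 20% stratum.

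**Conclusion.** The concern is factually right and of no consequence. Planned and reported precision differ by 5.13 − 5.00 = 0.13 points, at a 70% response rate, in subpopulation C only. The plan claims 5% at about 70%, and 5.13 agrees with that at the resolution stated. Planning with the normal approximation and reporting a score interval is a common and acceptable combination.

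Rewording would alter neither the sample size, nor the interval, nor any result or conclusion. The report will show the actual limits, so a reader will see the precision achieved. In the protocol, a new sentence would also need a written amendment with ethics approval under section 11.1, across about 250 centres in 30 countries, which is out of proportion to a tenth of a point.

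This rests on three assumptions: the 5% is a half-width (supported by the exact reproduction of 323), C recruits to about 323, and few dosed patients lack any post-baseline DLQI score. A rate in C well below 70% would widen the interval to at most about 5.6 points, with 0.12 of that due to the method.

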10.1 Regulatory and ethical compliance

This clinical study was designed and shall be implemented and reported in accordance with the ICH GCP, with applicable local regulations (including European Directive 2001/20/EC, and with the ethical principles laid down in the Declaration of Helsinki.

10.2 Informed consent procedures

Eligible patients may only be included in the study after providing written (witnessed, where required by law or regulation), IRB/IEC-approved informed consent, or, if incapable of doing so, after such consent has been provided by a legally acceptable representative of the patient. In cases where the patient's representative gives consent, the patient should be informed about the study to the extent possible given his/her understanding. If the patient is capable of doing so, he/she should indicate assent by personally signing and dating the written informed consent document or a separate assent form. Informed consent must be obtained before conducting any study-specific procedures (i.e. all of the procedures described in the protocol). The process of obtaining informed consent should be documented in the patient source documents.

Novartis will provide to Investigators in a separate document a proposed ICF that complies with the ICH GCP guideline and regulatory requirements and is considered appropriate for this study. Any changes to the proposed consent form suggested by the Investigator must be agreed to by Novartis before submission to the IRB/IEC, and a copy of the approved version must be provided to the Novartis monitor after IRB/IEC approval.

Women of child bearing potential should be informed that taking the study drug may involve unknown risks to the fetus if pregnancy were to occur during the study and agree that in order to participate in the study they must adhere to the contraception requirement for the duration of the study. If there is any question that the patient will not reliably comply, they should not be entered in the study.

10.3 Responsibilities of the investigator/qualified site staff and IRB/IEC

Before initiating a study, the Investigator/institution should obtain approval/favorable opinion from the IRB/IEC for the study protocol, written ICF, consent form updates, patient recruitment procedures (e.g. advertisements) and any other written information to be provided to patients. Prior to study start, the Investigator is required to sign a protocol signature page confirming his/her agreement to conduct the study in accordance with these documents and all of the instructions and procedures found in this protocol and to give access to all relevant data and records to Novartis monitors, auditors, Novartis Clinical Quality Assurance representatives, designated agents of Novartis, IRBs/IECs, and regulatory authorities as required. If an inspection of the study center is requested by a regulatory authority, the Investigator must inform Novartis immediately that this request has been made.

